H&P	History & Physical Exam
HRQOL	Health-related Quality of Life
HRPP	Human Research Protections Program
IHC	Immunohistochemistry
IV (or iv)	Intravenously
mRCC	Metastatic Renal Cell Cancer
MTD	Maximum Tolerated Dose
NCI	National Cancer Institute
ORR	Overall Response Rate
OS	Overall Survival
PBMCs	Peripheral Blood Mononuclear Cells
PD	Progressive Disease
PFS	Progression Free Survival
p.o.	Per os/by mouth/orally
PR	Partial Response
PRN	“Pro re nata” or as needed
QoL	Quality of Life
RR	Response Rate
RT	Room Temperature
SAbR	Stereotactic Ablative Body Radiotherapy
SAE	Serious Adverse Event
SBRT	Stereotactic Body Radiation Therapy
SD	Stable Disease
VAS	Visual Acuity Score
WBC	White Blood Cells

STUDY SCHEMA

STUDY SUMMARY

Title	Phase II Trial of Nivolumab and Stereotactic Ablative Radiation Therapy (SAbR) for Metastatic Clear Cell Renal Cell Carcinoma (mRCC)
Short Title	Nivolumab and SABR for metastatic RCC
Protocol Number	STU 122015-052
Phase	Phase II
Methodology	Single arm
Study Duration	8 years (5 years for enrollment and 3 years for follow-up).
Study Center(s)	Single-center at UTSW
Objectives	To evaluate safety and response rate (RR) of mRCC after treatment with SAbR and Nivolumab
Number of Subjects	21 patients
Diagnosis and Main Inclusion Criteria	Metastatic Clear Cell Renal Cell Carcinoma patients who have failed one anti-angiogenic therapy
Study Product(s), Dose, Route, Regimen	Nivolumab (brand name Opdivo): Nivolumab administered per standard of care according to institutional guidelines. The standard FDA approved administration and indications of Nivolumab is listed in the FDA website: www.fda.gov or Package Insert https://www.accessdata.fda.gov/drugsatfda_docs/label/2018/125554s058lbl.pdf ; SABR, dose variable, in 1-3 fractions.
Duration of administration	Nivolumab: Nivolumab administered per standard of care according to institutional guidelines. The standard FDA approved administration and indications of Nivolumab is listed in the FDA website: https://www.accessdata.fda.gov/drugsatfda_docs/label/2018/125554s058lbl.pdf ; SABR: 1-3 fractions over one week.
Reference therapy	Nivolumab alone from published historical control phase III study

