The relative levels of different monocyte subpopulations in the tumor biopsy sample after treatment as well as in the peripheral circulation often dictate the overall outcome of an immune response, and has been reported in previous immunotherapy trials [55]. Exploration of possible mechanisms of treatment failure can be explored from this analysis as well. Therefore the following subpopulation of cells will be quantified in patient PBMCs (and in tumor biopsy samples where applicable) collected before and after treatment utilizing some of the listed markers specific for those cells:

Immune Cells	Markers
--------------	---------

Lymphocytes	
Cytotoxic T Lymphocyte (CTL)	CD3, CD8
NK	CD3-, CD8, CD16, CD56, CD11b
NKT	CD3, CD16, CD1d
Helper T Cells	CD3, CD4
Th1	IL-18 receptor α , CXCR3, T cell Ig domain, TIM-3, T-bet
Th2	T1/ST2, TIM-1, TIM-2, GATA-3
Th17	Unknown, differentiated by IL-17 production, ROR- γ T
Treg	CD4+CD25+FoxP3+
Memory T Cells	CD45RO
TCM	CD4/CD8, CD62L, CCR7
TEM	CD4/CD8, CCR7-, CD45RA-, CD27
B Cells	CD19, mIg, FcR, CR, CD3-, HLA-DR
MDSC	CD14+, CD11b, CD33, CD 15, CD4, CD8-, HLA-DR-/low
Neutrophils	FcR, CR-, CD3-, HLA-DR-, GR-1 ^{high} , CD11b, Ly6G
Macrophages	FcR, CR, HLA-DR, GR-1 ^{mid}
DC	
Myeloid DC-1	CD11c, TLR2, TLR4
Myeloid DC-2	CD 141, TLR2, TLR4
Plasacytoid DC	CD303, TLR7, TLR9

Table 1: PBMC subpopulations and their markers.

Additionally, we plan to specifically quantify the expression of PD-L1 in all tumor samples from patients' pre-treatment tumor biopsies. Tumor PD-L1 membrane expression ($\geq 1\%$ vs. $< 1\%$ and $\geq 5\%$ vs. $< 5\%$) will be quantified in sections which have at least 100 tumor cells as assessed with immunohistochemical staining. It has been shown previously that tumors with higher PD-L1 expression have worse outcomes but it remains to be shown whether these tumors respond better to anti-PD-1 therapy. It would be very interesting to examine the correlation between PD-L1 expression and tumor response to the combination therapy.

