9.1 Sample Collection Guidelines

Samples will be labeled with the subject's de-identified study number and collection date and delivered for analysis during regular business hours to: NC7: 208; Attn [name]

9.1.1 Whole blood sample: Patient's whole blood will be collected in EDTA (Lavender top) tubes for ~ 40-50 ml. In addition, ~10 ml will be collected in anti-coagulant-free tubes (Red top) for the collection of sera. The blood will immediately be processed (within 2 hours) by centrifugation (1000 g, 15 min, 4°C), collecting the supernatant and freezing at -80°C in 5 aliquots for future experiments. The pellet will be re-suspended in PBS and PBMC will be isolated using standard protocol. Briefly, the cell suspension will be carefully placed on 10ml polystyrene tube containing 1ml ficoll and centrifuged (400g, 30min, RT). PBMC region will be collected from the ficoll and washed 3x with PBS. Cells will be counted and frozen in 5 aliquots with 10% DMSO, 90% FBS at -80°C.

9.1.2 Tumor Biopsy Sample: A CT-guided biopsy of tumor lesion consisting of 4-5 18G needle cores is recommended at the time of registration of the patients to

the study unless a biopsy has been done in the previous 12 months (See 5.1.15). A second biopsy at 8 weeks (+/- 2 week) is elective.

9.1.2.1

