- 9.2.4 Chromium Release Cytotoxicity Assays:** For cell-mediated cytotoxicity analysis, A 50 µl sample of ⁵¹Cr-labeled target cells (Caki-2 and ACHIN human renal cancer cells) is mixed with 100µl of effector cells (patient PBMC) at various target to effector ratio (E:T ratios). After centrifugation at 100 X G, the cells are incubated for 2 hr at 37°C. The radioactivity of culture supernatant is measured using a gamma counter and percentage of cytotoxicity is calculated. For antibody-dependent cytotoxicity analysis this procedure will be performed with patient's plasma instead of PBMC and the percentage of cytotoxicity is calculated in similar manner. An alternate and non-radioactive labeling method utilizes GAPDH enzyme release from lysed cells called Bioluminescence Non-Radioactive Cytotoxicity Assay (aCella-TOX, T Cell Technology, INC) [108, 109].
- 9.2.5 Flow cytometric analysis (FACS):** For FACS analysis of cell-surface molecules, the cell samples are stained with fluorescent dye – conjugated monoclonal antibodies against the selected markers on ice followed by fixation with 4% paraformaldehyde. Data are acquired on a LSRII (BD Biosciences) and analyzed using FACSDiva software (BD Biosciences). The PBMC of each patient before and after treatment will be analyzed to identify the relative sub-population of CTLs, regulatory T-Cells, effector memory T cells, MDSCs, neutrophils and NK cells utilizing appropriate cell surface markers.

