- 9.2.6 Immunohistochemical staining (IHC):** Standard immunohistochemistry staining procedure for will be performed using the Benchmark XT automated stainer (Ventana) for both antibodies. Briefly, formalin-fixed, paraffin-embedded tissue sections will be cut at 3-4 micron and air-dried overnight. The sections will be deparaffinized, rehydrated, and subjected to heat-induced epitope retrieval. Sections will then be incubated with appropriate primary antibody. For signal detection, ultraView universal detection system (Ventana) will be used. The slides will be developed using 3-3'-diaminobenzidine chromogen and counterstained with hematoxylin. Appropriate positive and negative controls will be utilized for each run of immunostains. The evaluation of the immunostaining will be carried out by a genitourinary pathologist without knowledge of any clinicopathologic data. Only nuclear reactivity will be considered positive. An H score will be assigned as the product of average intensity of staining (0 for negative, 1 for weakly positive, 2 for moderately positive, and 3 for strongly positive) and extent of immunoexpression (0-100% percentage of cells staining). In addition, Dual-antibody ISH will be performed to identify and analyze TILs, CTL (CD3+,CD8+), Tregs (CD4+FoxP3), DC (CD11c) , NK/T (CD3+, CD1d), neutrophils (CD11b, Ly6G} and MDSC (CD14+,CD11b) in the tumor tissue before and after treatment, when available. PD-L1 expression will be quantified from biopsies of tumors prior to treatment.

9.2.7 Serum Cytokine Analysis: Multiplex cytokine analysis in patient's plasma will be performed in precoated 96 well plates (Human TH1/TH2 10 plex ultrasensitive assay, Meso Scale Discovery – MSD, Maryland, USA) according to manufacturer's instructions. 25 µL of diluent 2 is dispersed into each well. The plate is sealed and incubated by vigorous horizontal shaking for 30 minutes at RT.

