11.3 Data Analyses Plans

Exact binomial method will be used to calculate the response rate, toxicity rate, CR rate, and the corresponding 95% confidence interval. [Exact binomial test will be used to investigate if the response rate of the treatment arm is significantly different from that of historical control.](#) PFS and OS will be estimated using the Kaplan-Meier approach along with the 95% confidence interval using Greenwood's formula. One sample log-rank tests will be conducted to investigate if OS or PFS in the treatment arm is significantly different from that of historical control.

Generalized estimating equation (GEE) analysis will be conducted to investigate if there are significant changes in surrogate makers such as CD25, CD71, CD45RO, CD107a, CD54, CD69, Ki67, ICOS/CD278 and PBMC over time. HRQoL, CEA and quality adjusted survival time analysis is described in Section 10.

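### Blood neutrophils are to be compared before and after treatment in frozen ficoll-separated PBMC, a specimen that cannot be read as the circulating neutrophil fraction

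*Combined protocol and SAP*

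**What the plan says.** Section 9.2.5 describes the flow cytometry: "The PBMC of each patient before and after treatment will be analyzed to identify the relative sub-population of CTLs", and the list continues to "effector memory T cells, MDSCs, neutrophils and NK cells utilizing appropriate cell surface markers". Section 1.5 sets out the same intention. It says that the "subpopulation of cells will be quantified in patient PBMCs (and in tumor biopsy samples where applicable) collected before and after treatment", and the table that follows (Table 1, captioned as PBMC subpopulations) has a neutrophil row.

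Section 9.1.1 describes how those cells are obtained. EDTA blood is centrifuged, the supernatant is removed, and the pellet is resuspended and layered on ficoll. Then "PBMC region will be collected from the ficoll and washed 3x with PBS", and "Cells will be counted and frozen in 5 aliquots with 10% DMSO, 90% FBS at -80°C". No whole-blood, red-cell-lysed or granulocyte aliquot is set aside for flow cytometry. The List of Abbreviations expands PBMC as "Peripheral Blood Mononuclear Cells".

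Neutrophils appear once more, in section 9.2.6, as one of the populations to be stained together with "MDSC (CD14+,CD11b) in the tumor tissue before and after treatment, when available". That is a tissue measurement, not a blood measurement.

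**The concern.** Neutrophils are polymorphonuclear, so they fall outside the protocol's own definition of the specimen in which they are to be counted. A number will still come off the cytometer, because some granulocytes carry over into the ficoll layer. That number can move between visits with the quality of the gradient and the thaw, without any change in the patient. In a trial planned for 19 evaluable patients, with 21 to be accrued, a technical shift between draws could be reported as a treatment-related change in circulating neutrophils. Section 1.5 says that this analysis may be used to explore mechanisms of treatment failure, so a spurious shift could be given a biological reading.

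**Working it through.** The plan states no figure for this readout, so there is nothing to reproduce. The check traces the specimen and then illustrates the scale.

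**Trace of the specimen**

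| Step | Section | What it gives |
|---|---|---|
| Analyte | 9.2.5; 1.5, Table 1 | Relative neutrophil sub-population, before and after treatment |
| Specimen | 9.2.5; 1.5 | PBMC |
| Definition of specimen | List of Abbreviations | Mononuclear cells |
| Preparation | 9.1.1 | Ficoll at 400 g for 30 min; only the PBMC layer kept, washed three times |
| Storage | 9.1.1 | Counted cells frozen in 5 aliquots |
| Other blood source of neutrophils | 5.1.9, 5.2.2, 5.4 | Hematology only recommended at screening; labs other than the correlative draws at the oncologist's discretion; no blood-count row in the events table; nothing links a differential to the correlative analysis |
| Tumor tissue | 9.1.2, 9.2.6 | Staining when tissue is available; only the elective 8-week biopsy is prepared for flow, without a ficoll step |

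No step supplies a specimen that retains blood neutrophils.

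**Illustration of scale (both inputs are assumptions, not in the documents)**

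Let r be the true neutrophil-to-mononuclear ratio in blood, and c the share of neutrophils carried into the ficoll layer. Then

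- true neutrophil share = r / (1 + r)
- measured share in the layer = c·r / (c·r + 1)

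| r | True share | c = 0.1% | c = 1% | c = 5% |
|---|---|---|---|---|
| 1.5 | 60% | 0.15% | 1.48% | 6.98% |
| 3 | 75% | 0.30% | 2.91% | 13.04% |

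For example, with r = 1.5 and c = 1%: 0.015 / 1.015 = 1.48%. Doubling r at c = 1% takes the reading from 1.48% to 2.91%, about a doubling. Holding r = 1.5 and letting c run over the assumed range takes it from 0.15% to 6.98%, more than 40-fold. That spread follows from the assumed 50-fold range in c and does not estimate how much carry-over would vary in this laboratory. It does show that the reading is roughly proportional to c. A before/after ratio is therefore interpretable only if carry-over is stable, and nothing in the protocol measures or controls it.

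**Effect on the other subsets**

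Section 9.2.5 does not define the denominator of a relative sub-population. Take the unfavorable case of all cells in the layer, and suppose contamination rises from 1% to 5% (assumed). A subset at 30% of mononuclear cells would read 0.30 × 0.99 = 29.7% and then 0.30 × 0.95 = 28.5%. The relative change is 1 − 0.95/0.99 = 4.0%.

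**The case against.** The behavior of neutrophils on ficoll and through freezing is general laboratory knowledge and not stated in the documents. The inputs to the illustration are invented, and nothing shows that carry-over varies widely under one fixed procedure. Both points stand. The mismatch between analyte and specimen is in the documents; its size is not.

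A reader might infer that every neutrophil is lost from every sample. The documents do not support that. A gradient depletes neutrophils without necessarily removing all of them, and a low-density granulocyte residue can remain. The residue still does not estimate the blood fraction.

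A reader might also infer that contamination spoils the other PBMC percentages. The calculation above gives about 4% relative in an assumed unfavorable case, and even that needs a denominator the plan does not define.

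Finally, a reader might infer that a named endpoint is compromised. Section 2.4.4 defines immune response by ELISpot, T-cell proliferation and ELISA. Objective 2.3.2 names PD-L1, DC-HIL in MDSC and TCR measures, with an open-ended list but no mention of neutrophils. The GEE analysis in section 11.3 ends its marker list with "ICOS/CD278 and PBMC over time", again without naming neutrophils. This part of the objection stands in full and confines the point to one exploratory readout.

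**Conclusion.** The point holds in a narrow form. As written, the before/after neutrophil comparison in PBMC is not a valid measure of circulating neutrophils, because the specimen is defined and prepared as mononuclear cells and no alternative specimen is named. That conclusion rests on the protocol's own text plus one assumption from general laboratory knowledge: that ficoll separation and freezing strongly deplete neutrophils.

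The size of the resulting error cannot be computed from the documents; the table above only illustrates it. The CTL, Treg, memory T and NK readouts are essentially unaffected. So are tissue staining, response rate, PFS, OS and the sample size. This is a minor correction, worth making because it is nearly free and prevents a spurious exploratory finding.

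**What to change.** 1. Delete neutrophils from the PBMC list in section 9.2.5.
2. State under Table 1 that its neutrophil row applies to tumor tissue only. The row should not be removed, because section 1.5 extends the list to biopsies and section 9.2.6 plans tissue staining.
3. If circulating neutrophils are of interest, take the absolute count and the neutrophil-to-lymphocyte ratio from the standard-of-care blood count differential nearest each correlative draw, where one exists. Report how many draws have one.
4. Report the remaining PBMC subsets as a percentage of gated live mononuclear cells, which also settles the undefined denominator.

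The cost is laboratory wording plus transcription of existing results, with no extra blood. The downside is missing data. A paired differential is not guaranteed, since hematology is only recommended, other labs are discretionary, and nivolumab may be given in community practice (section 4.2.1). Circulating neutrophil data will therefore be absent for some draws. Staining a whole-blood aliquot before the gradient would avoid that gap, but it adds same-day laboratory work at every draw.

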2.3 Exploratory Objectives

- 2.3.1 To measure treatment-related tumor-specific immune response (immunogenicity).
- 2.3.2 To explore the immunological biomarkers (PD-L1 expression in tumor, DC-HIL expression in MDSC, TCR diversity and clonality, etc) as correlates or predictors for treatment response.
- 2.3.3 To evaluate the cost-effectiveness and cost-utility of the addition of SABR to Nivolumab in patients with mRCC

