25 µL of the patient plasma is added per well and all samples measured in triplicates. Plates are sealed and incubated by vigorous horizontal shaking for two hours at RT. Plates are washed three times with 0.05% Tween 20 in PBS. 25 µL of 1× detection antibody solution is placed per well and sealed plates are incubated by vigorous horizontal shaking for two hours at RT. Plates are washed three times with 0.05% Tween 20 in PBS. 150 µL of 2× Read Buffer T is added to each well. Plates are analysed using the MSD SECTOR Imager 2400 and Discovery Workbench 3.0 software (both from Meso Scale Discovery, USA). The mean value of two wells is taken as the recorded reading, provided that the coefficient of variation (CV) was less than 10%. Concentrations recorded lower than the standard curve are kept as absolute values. For purposes of logarithmic analysis, readings of 0 are adjusted to 0.01 pg/ml. The following cytokines will be measured before and after treatment for each patients: Th1/Th2/Th17 cytokines, IFN-γ, IL-1β, IL-2, IL-4, IL-5, IL-8, IL-10, IL-12p70, IL-13, IL-17 TNF-α; pro-inflammatory cytokines: GM-CSF, IFN-γ, IL-1β, IL-2, IL-6, IL-8, IL-10, IL-12p70, TNF-α; Chemokines: Eotaxin, MIP-1β, TARC, IP-10, IL-8, MCP-1, MCP-4 and others including IL-6, TGF-β and HMGB1 (see section 1.5).

9.2.8 Western-blot/Immuno-blot: Caki-2 and ACHIN human renal cancer cells lysate will be used to perform immune-blott using plasma collected from patients before and after treatment. The Caki-2 and ACHIN cell 10⁶ cells/mL will be lysed in immunoprecipitation assay buffer on ice for 30 min. Standard western blott methodology will be utilized. Briefly, 400 µg of protein will be separated using pre-made gradient 4% to 12% Bis-Tris gels (Invitrogen, Burlington, ON, Canada) and transferred to nitrocellulose. Patient sera/plasma will be diluted 1/500 in Blotto (5% dry milk powder; 0.1% Tween 20; 50 mmol/L Tris; 150 mmol/L NaCl) and incubated with nitrocellulose membranes for 1 h at room temperature using a multichannel immublotting device (Mini Protean II Multiscreen, Bio-Rad, Mississauga, ON, Canada). The membrane will then incubated for 1 h at room temperature with horseradish peroxidase–conjugated goat anti-human IgG (H+L; Jackson ImmunoResearch, West Grove, PA) diluted 1/10,000 in Blotto and visualized by enhanced chemiluminescence.

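### One constant, 0.01 pg/ml, replaces every zero cytokine reading in log analysis; for analytes whose assay limit is well above it, a few zeros can dominate the exploratory fold changes

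*Combined protocol and SAP*

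**What the plan says.** Section 9.2.7 (Serum Cytokine Analysis) holds the only data-handling rules for cytokines. Readings below the curve are retained: "Concentrations recorded lower than the standard curve are kept as absolute values". Zeros get a fixed substitute: "For purposes of logarithmic analysis, readings of 0 are adjusted to 0.01 pg/ml". The same constant serves every analyte. No detection or quantification limit is given for any of them, and there is no censored-data or rank method and no sensitivity analysis to the constant.

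The comparison is within patient: "The following cytokines will be measured before and after treatment for each patients". Section 11.3 plans a GEE for changes in surrogate markers over time, but its list names cell markers and PBMC and no cytokine. The related objectives in section 2.3, such as "To measure treatment-related tumor-specific immune response (immunogenicity"), are exploratory. Section 11.2 plans 19 evaluable patients.

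**The concern.** Two samples that are both too low to quantify can receive very different log values, depending only on whether the reader returned 0 or a small positive number. If the smallest quantifiable reading for an analyte is far above 0.01 pg/ml, a move from 0 to just detectable counts as a very large fold change, although the assay shows only that the first sample was below its limit.

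Section 1.5 wants the cytokines to show which immune pathways the treatment starts or inhibits. With about 19 pairs, a few zeros could decide which cytokine appears to change and by how much, and the size of that effect would come from the chosen constant.

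**Working it through.** **Number of pairs.** The plan's figure of 19 reproduces. With an upper rejection region of 8 or more responses out of 19, the tail probability is 0.0775 at a 25% response rate (0.10 allowed per tail), and power is 0.820 at 50%. Here 19 serves only as the number of before/after pairs; section 9.2.7 states no sample size or error rate.

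**Size of one artefact.** A substituted zero paired with a detected value x gives an apparent fold change of x/0.01. The documents give no limits, so x is an assumption:

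| x (pg/ml) | x/0.01 | Multiplier of the geometric mean ratio, 1 baseline zero in 19 | 4 baseline zeros in 19 |
|---|---|---|---|
| 0.02 | 2 | 1.04 | 1.16 |
| 0.05 | 5 | 1.09 | 1.40 |
| 0.1 | 10 | 1.13 | 1.62 |
| 0.5 | 50 | 1.23 | 2.28 |
| 1 | 100 | 1.27 | 2.64 |

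The multiplier is (x/0.01)^(k/19) for k zeros. At x = 0.5 one zero adds log10(50) = 1.70 to that patient's change. With an assumed SD of change of 0.25 log10, that is 1.70/0.25 = 6.8 SDs. The mean moves by 1.70/19 = 0.089, and 10^0.089 = 1.23.

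**Where the zeros fall.** Assume a true 1.5-fold rise, SD of ln change 0.6, limit 0.5 pg/ml, two pairs with a zero, and a paired t-test at two-sided 5%. Power with no zeros is 0.80.
- Both zeros at baseline: ratio 1.5 × 1.51 = 2.27, power 0.85.
- Both after treatment: ratio 1.5 / 1.51 = 0.99, power about 0.
- Split at random: ratio 1.50, power 0.23. Half-limit substitution gives 0.74.

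Balanced zeros therefore cost precision only, and unbalanced zeros bias the estimate in either direction.

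**Zeros arising from the concentrations.** Assume 19 pairs, a true 1.5-fold rise, SD of change 0.25 log10, baseline SD 0.4 log10, and a baseline median of 2 or 1.4 times the limit. The share of baselines below the limit is then Φ(−log10(2)/0.4) = Φ(−0.75) = 23%, or Φ(−log10(1.4)/0.4) = Φ(−0.37) = 36%. A quarter to all of the below-limit readings are returned as 0, at random, or only the lowest of them are. Simulated results with a paired t-test, good to within a few percentage points:

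| Assumed limit (pg/ml) | Power, rule as written | Power, half-limit substitution |
|---|---|---|
| 0.5 | 36-51% (zeros at random); 61-64% (only the lowest read 0) | 79-82% |
| 0.1 | 53-64% (zeros at random); up to about 74% overall | 80-81% |
| 0.05 | 68-74% (zeros at random) | about 80% |
| 0.02 | 80-81% (zeros at random) | 80-81% |

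At 0.5 pg/ml with zeros at random, the estimated ratio is 1.59 to 2.13 under the rule as written, against about 1.52 with half-limit substitution. A real rise leaves more zeros at baseline than afterwards, so in this setting the estimate is inflated while power falls. With no true change, type I error is about 3-5%. In the fixed-count model above it is about 1-6%.

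**The case against.** The strongest reply is that the harm is conditional and its conditions are unknown. It needs assay limits well above 0.01 pg/ml and an appreciable number of exact zeros; bias also needs zeros unevenly spread between visits. The documents give none of these figures, and the named kit is described as "Human TH1/TH2 10 plex ultrasensitive assay". At a limit of 0.02 pg/ml the rule as written costs nothing. Retaining below-curve readings also presupposes that many of them are not zero, so scenarios in which all read 0 are extreme. The paired t-test is an assumption too: no document names a cytokine test, and a signed-rank test on the same data at a limit of 0.5 pg/ml keeps power at about 61-76% with zeros at random and 81% when only the lowest quarter of below-limit readings are 0. All of this stands and limits the claim.

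Half-limit substitution is itself an arbitrary constant: with no true change it gave 1.02- to 1.06-fold. That also stands, and it is why a censored or rank-based method is preferable.

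Three stronger readings are tempting but not supported. A reader might infer that undetectable samples always distort the estimate and hide real changes; balanced zeros leave the ratio unbiased, and baseline zeros exaggerate a rise. A reader might infer false pathway signals when nothing changes; type I error is not inflated. A reader might infer that low readings drop out selectively through the 10% coefficient-of-variation condition; the section does not say what happens to readings that fail it.

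**Conclusion.** The point holds as a conditional weakness in an exploratory analysis. Using one constant for every analyte is an avoidable choice, and nothing elsewhere in the plan offsets it. For analytes with limits of about 0.05 pg/ml or more and some exact zeros, the loss can be material: power of about 36-64% at 0.5 pg/ml and 53-74% at 0.1, against about 80% with half-limit substitution. Near 0.02 pg/ml it vanishes. These figures rest on the assumed limits, share of zeros, effect, SD and test shown above.

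The primary response-rate analysis is untouched, and section 2.4.4 defines immune response by ELISpot, T-cell proliferation and ELISA, not by cytokines. The questions of which two of three wells are averaged, what follows a failed coefficient of variation, and how a 10-plex kit covers the longer analyte list are separate clarifications. They form no part of this conclusion.

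**What to change.** Replace the two sentences in section 9.2.7 with one rule. For log-scale analysis, all readings below an analyte's lower limit, including 0, are treated as left-censored at that limit and analysed with a censored model or a rank-based test; half-limit substitution for every such reading is a simple alternative. State the limit for each analyte, report the share of readings below it by visit, and report mainly undetectable analytes as percent detectable. Settle the rule before the cytokine data are analysed, so that it does not depend on the results.

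The cost is a few sentences and a few lines of analysis code, with no new samples. Some low-end information is lost, half-limit substitution carries a small bias of its own, and some analytes will be reported only as detectable or not.
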